### Study Protocol - Proactive Prophylaxis With Azithromycin and Chloroquine in Hospitalised Patients With COVID-19 (ProPAC-COVID)

*A Randomised, Good-Clinical-Practice-monitored, Placebo-controlled, double-blinded study to clarify whether hospital length and risk of intensive care stay may be reduced in hospitalized patients who have COVID-19 treated with azithromycin and hydroxychloroquine for 15 days after inclusion.*

**Hypothesis:**

→ In patients with urgent hospital admission and a positive test SARS-CoV-2 treatment with hydroxychloroquine azithromycin leads to shorter hospitalisation and fewer admissions to the intensive care unit.

### **Azithromycin**

Categorized as an antibacterial agent. The drug is an approved, and marketed in Denmark, for treatment of upper and lower respiratory tract infection. Azithromycin is also, according to available evidence and current guidelines, used for treatment of asthma, COPD and bronchiectasis in order to improve disease control and reduce exacerbation rate. Please see enclosed product summaries for further information.

### **Hydroxychloroquine:**

Categorized as an anti-inflammatory and anti-malaria agent.

The drug is approved and marketed in Denmark for the prevention and treatment of malaria, for the treatment of rheumatoid arthritis, discoid and systemic lupus erythematosus and juvenile idiopathic arthritis.

Manufacturing, packaging and labelling of IMP:

The trial drugs (IMP) are manufactured by Glostrup pharmacy by pharmacist [name]. Placebo capsules are thus made similar to the intervention medicine. The drug (and Placebo) are labelled, according to Appendix 13. Glostrup pharmacy has a key for blinding. Therefore, it will always be possible to unblind a patient if indicated. Investigator must notify sponsor on grounds if a patient is unblinded.

Medical professionals dispense the IMP daily during hospitalization, except for patients preferring to handle their medication themselves. In the latter case, patient will fill in a medication diary (provided at randomisation). For all patients who are discharged during the intervention period, a medication diary will be provided. The medication diary is subsequently collected.

Exactly the amount of medication or placebo that the patient is required to take during the study periode will be provided, but for patients who do not take all the medication (protocol deviation), the remaining medication will be collected by the study staff. The patient will receive a follow-up phone call to check whether they have adhered to the medication schedule according to the trial protocol.

# Proactive Prophylaxis With Azithromycin and Chloroquine in Hospitalised Patients With COVID-19 (ProPAC-COVID)

## 1. Hypothesis and aims:

### 1.1 Hypothesis:

In patients with acute hospital admission, a positive test for 2019-nCoV and symptoms of COVID-19 disease, treatment with virus-modifying agent hydroxychloroquine as well as virus-immunomodulatory and antibacterial drug azithromycin can lead to shorter hospitalisation and fewer admissions to the intensive care unit.

### 1.2 Aims:

The aim of this randomised GCP-controlled trial is to clarify whether combination therapy with macrolide azithromycin and hydroxychloroquine via anti-inflammation/immune modulation, antiviral efficacy and pre-emptive treatment of supra-infections can shorten hospitalisation duration (measured as "days alive and out of hospital" as the primary outcome), reduce the risk of non-invasive ventilation, treatment in the intensive care unit and death.

## 2. Background and scientific perspective:

### 2.1 Background - rationale

#### *Coronavirus - COVID-19*

In the ongoing coronavirus pandemic, COVID-19, with its origin in Wuhan, China, there is still sparse data on the course, risk of various complications, and the best possible treatment of patients admitted to hospital to ensure best possible survival and reducing length of stay at hospital. The most frequent symptoms are fever (> 80%) and cough (70-80%), together with radiologically findings of "ground-glass infiltrates" or "patchy infiltrates" in the patients with the most severely ill patients (86%), compatible with severe viral pneumonitis (1, 2). The length of hospitalisation is observed to be relatively long, 10-15 days (3), which in itself is a problem as hospitals can quickly reach the maximum capacity for hospitalisation and the proportion of patients who become critically ill have, based on the observations reported so far, had a mortality rate of > 60% (4), and overall mortality for admitted patients in China with COVID-19 infection is apparently unusually high for viral respiratory tract infections with an estimate of 25% (2).

#### *COVID-19 and lung disease*

Only specific data on patients with Chronic Obstructive Pulmonary Disease (COPD) have been reported in a few studies, but the risk of in-hospital death appears to be very high (OR 5.4 [95% CI 0.96-30.40]) (2).

#### *Lack of specific treatment*

## Proactive Prophylaxis With Azithromycin and Chloroquine in Hospitalised Patients With COVID-19 (ProPAC-COVID)

Despite the rapid spread of the disease globally, there is no solid data yet to recommend any specific treatments, and by that, symptomatic, organ supportive therapy is recommended, and in case of progression to severe acute respiratory failure mechanical ventilation (5). A high incidence of bacterial super-infections has been reported in patients with COVID-19 who died (50%) compared to survivors (1%) ( $p < 0.0001$ ), and likewise, an incidence of septic shock of 70% and 0%, respectively (2). Thus, there is an urgent need for treatments that can improve the course of the diseases in the individual patients, including positive impact on risk for hospital admission, duration of hospitalisation, risk of secondary infections and death.

### *Macrolide azithromycin as a possible treatment for patients with COVID-19*

Azithromycin is a macrolide antibiotic that has shown convincing efficacy in several studies in recent years to reduce hospitalisation-related exacerbations in COPD (6, 7), and to reduce exacerbation rate in asthma (8) and non-cystic fibrosis bronchiectasis (9). At the same time, it has been shown that azithromycin has a distinct effect by down-regulating airway inflammation by reducing CXCL1, TNF-alpha, IL-13 and IL-12p40 (10). Furthermore, a strong association has also been reported between survival from Acute Respiratory Distress Syndrome (ARDS) and administration of azithromycin (HR for 90 days of death for all causes: 0.49 [95% CI 0.27 - 0.87] in a well-conducted study (11).

Furthermore, it has been consistently observed in several recent publications that azithromycin itself appears to have an antiviral effect on a number of several viruses causing respiratory tract infections, such as Respiratory Syncytial Virus (RSV) (12), Rhinovirus (13) and Zika virus (14).

### *Hydroxychloroquine as immunomodulatory and antiviral agent by COVID-19*

Hydroxychloroquine has been marketed since 1934, originally developed for prophylaxis and treatment of malaria, but has for years also been used as an anti-inflammatory agent for rheumatic diseases. Large daily doses (up to 400 mg a day) of hydroxychloroquine are prescribed over many years to patients with arthritis such as systemic lupus erythematosus and rheumatoid arthritis for anti-inflammatory purposes, which is generally well-tolerated (16). but in addition to these effects, it is well described that the drug has an antiviral effect especially against flavivirus, retrovirus and coronavirus by inhibiting a number of low-pH-dependent steps in virus replication, as well as by inhibiting the pH-dependent endosomal mediated viral uptake in cells (15). The drug is well tolerated even with high dosage, for up to five years and there is no signal for birth defects with usage of the drug summarised by Savarino et al. (15).

Cell studies with primate cells infected with the coronavirus that induced SARS-1 (formerly called SARS) have shown that chloroquine, in a dose-dependent manner, inhibits the ability of the corona virus to infect cells and to spread among cells (17). Thus, several researchers and health care professionals have, during the present SARS-CoV-2 pandemic, have proposed studies examining hydroxychloroquine/chloroquine as treatment for patients with COVID-19 disease (18, 19).

# Proactive Prophylaxis With Azithromycin and Chloroquine in Hospitalised Patients With COVID-19 (ProPAC-COVID)

## 2.2 Scientific perspective for this study

The study will clarify whether treatment with azithromycin in combination with hydroxychloroquine for 15 days from the time of hospital admission with diagnosed COVID-19 disease may reduce the length of hospitalisation, the risk of admission to the intensive care unit, treatment with non-invasive ventilation and death. The study will also clarify whether this treatment can reduce the need for oxygen supplementation (time for breathing on its own without oxygen supplementation) or for regular Long-Term Oxygen Therapy oxygen supplementation ("home oxygen").

If the treatment also improves the course of COVID-19 disease in patients with pre-existing lung disease, a very large number of patients could benefit from the treatment immediately.

The study originates from the Danish national non-commercial lung research network COP:TRIN (Chronic Obstructive Pulmonary Disease: Trial Network).

## 3. Method:

### 3.1 Design:

Randomised, Good-Clinical-Practice-monitored, placebo-controlled, double-blind study.

### 3.2. Recruitment and inclusion:

See point 12.

### 3.3 Inclusion:

#### Inclusion criteria:

- Patient admitted to Danish emergency departments, respiratory medicine departments or internal medicine departments
- Age  $\geq$  18 years
- Hospitalized  $\leq$ 48 hours
- Positive SARS-CoV-2 test / diagnosis during the hospitalization (confirmed).
- Men or non-fertile women. Fertile women\* must not be pregnant, i.e. negative pregnancy test must be available at inclusion
- Informed consent signed

\*Defined as after menarche and until postmenopausal (no menstruation for 12 months)

#### Exclusion criteria:

- At the time of recruitment, the patient uses  $>5$  LO2/min (equivalent to 40% FiO2 if measured)
- Known intolerance/allergy to azithromycin or hydroxychloroquine or hypersensitivity to quinine or 4-aminoquinoline derivatives

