## Proactive Prophylaxis With Azithromycin and Chloroquine in Hospitalised Patients With COVID-19 (ProPAC-COVID)

- Neurogenic hearing loss
- Psoriasis
- Retinopathy
- Maculopathy
- Visual field changes
- Breastfeeding
- Severe liver diseases other than amoebiasis (spontaneous INR > 1.5)
- Severe gastrointestinal, neurological and hematological disorders (investigator-assessed)
- eGFR <45 ml/min/1.73 m^2
- Clinically significant cardiac conduction disorders/arrhythmias or prolonged QTc interval (QTc (f) of > 480/470 ms).
- Myasthenia gravis
- Treatment with digoxin\*
- Glucose-6-phosphate dehydrogenase deficiency
- Porphyria
- Hypoglycaemia (Blood glucose at any time since hospitalization of <3.0 mmol/L)
- Severe mental illness which significantly impedes cooperation
- Severe linguistic problems that significantly hinder cooperation
- Treatment with ergot alkaloids

\*The patient must not be treated with digoxin for the duration of the intervention. For atrial fibrillation/flutter, select according to the Cardiovascular National Treatment Guide (NBV): Calcium antagonist, Beta blocker, direct current (DC) conversion or amiodarone. In case of urgent need for digoxin treatment (contraindication for the aforementioned equal alternatives), the test drug should be paused, and ECG should be recorded daily.

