### Drug Interactions

Interactions should be taken into account if the patient is taking other medications. For azithromycin, this includes antacids, ergotamine derivatives, colchicine and cyclosporine. For hydroxychloroquine, these include antidiabetic agents, tricyclic antidepressants, antipsychotics, halofantrine, cyclosporine, mefloquine, antiepileptic drugs, praziquantel and agalsidase.

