### 3.3.2. Allocation:

The sponsor generates a randomisation sequence. Randomisation will be in blocks of unknown size and the final allocation will be via an encrypted website (REDCap), where also inclusion and exclusion criteria are required to be filled in correctly in order to randomise a patient.

Allocation will be stratified for age (>70 years vs. <=70 years), site of recruitment and whether the patient has any of the following chronic lung diseases: COPD, asthma, bronchiectasis, interstitial lung disease (Yes vs. No).

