### 3.3.4 Intervention

Neither patients nor study staff will know which group the patient is allocated to. The medicine will be marked neutral, e.g. "Azithromycin group A" and "Azithromycin group B" and the same for Hydroxychloroquine.

NOTE: If the patient is receiving azithromycin prophylaxis, common practice is followed: the prophylaxis is paused and then restarted as usual.

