#### Hydroxychloroquine:

Furthermore, the patient will be treated with hydroxychloroquine as follows:

Day 1-15: 200 mg x 2

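### Current hydroxychloroquine or chloroquine users are neither excluded nor covered by a pause rule, so a control patient may stay on active drug and an intervention patient may take it twice.

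*Protocol*

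**What the plan says.** **Eligibility.** Among the exclusion criteria in Protocol section 3.3, hydroxychloroquine is named once: "Known intolerance/allergy to azithromycin or hydroxychloroquine or hypersensitivity to quinine or 4-aminoquinoline derivatives". Two current treatments are excluded, digoxin and, at the end of the list, "Treatment with ergot alkaloids". For digoxin the protocol adds a ban throughout the intervention and a contingency plan. The inclusion criteria do not mention earlier or current use of either study drug. Section 3.3.2 has the REDCap system hold the criteria, "where also inclusion and exclusion criteria are required to be filled in correctly in order to randomise a patient".

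**Interactions.** The Drug Interactions paragraph asks that other medicines be taken into account: "For hydroxychloroquine, these include antidiabetic agents, tricyclic antidepressants, antipsychotics, halofantrine, cyclosporine, mefloquine, antiepileptic drugs, praziquantel and agalsidase". Neither hydroxychloroquine nor chloroquine is in the list.

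**Patients already on a study drug.** Section 3.3.4 deals with one of the two drugs: "If the patient is receiving azithromycin prophylaxis, common practice is followed: the prophylaxis is paused and then restarted as usual". There is no counterpart for hydroxychloroquine.

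**Background use.** The protocol's product description says hydroxychloroquine is approved "for the treatment of rheumatoid arthritis, discoid and systemic lupus erythematosus and juvenile idiopathic arthritis". Section 2.1 adds: "Large daily doses (up to 400 mg a day) of hydroxychloroquine are prescribed over many years to patients with arthritis". The trial dose in section 3.3.4 is "Day 1-15: 200 mg x 2".

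**SAP.** Rheumatic diseases are listed among the baseline comorbid conditions, so such patients are expected. Under Medication during hospitalization the SAP lists non-study antibiotics, azithromycin among them, and days on corticosteroids. It has no entry for the patient's own hydroxychloroquine and no rule for analysing users.

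**The concern.** The protocol foresaw that some patients would arrive on one study drug and wrote a pause rule for it. For the other drug it wrote none, although its own text describes a group that takes that drug for years.

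Two things are at stake.

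- **Safety, the weightier one.** An intervention patient who keeps taking own hydroxychloroquine gets the drug from two sources, together with azithromycin. Section 6 lists QT prolongation for both drugs. Because treatment is blinded, staff cannot tell whether a patient on own supply is also receiving active trial drug.
- **The contrast.** Section 3.3.4 defines control treatment as standard care plus both placebos, and allows active study therapy only if it becomes standard treatment during the trial. Own long-term hydroxychloroquine is a different case, so a user in the control arm does not fit the definition of the comparator.

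**Working it through.** **1. Does any written rule stop a current user from being randomised?** Take a patient who tolerates hydroxychloroquine.

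| Place in the protocol | What it covers | Stops a tolerant user? |
|---|---|---|
| 3.3 Inclusion criteria | Age, setting, positive test, pregnancy, consent | No |
| 3.3 Exclusion: intolerance or hypersensitivity | Patients who cannot take the drug | No |
| 3.3 Exclusion: current treatments | Digoxin, ergot alkaloids | No |
| 3.3 Exclusion: retinopathy, maculopathy, visual field changes, psoriasis, eGFR below 45, long QTc | Conditions that some users have | Some users only |
| 3.3 Drug Interactions | Listed medicines, in general terms | No |
| 3.3.2 REDCap check | The same criteria | No |
| 3.3.4 Pause rule | Azithromycin prophylaxis | No |

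A user without one of the listed conditions meets every stated criterion.

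**2. Does any written rule stop own supply after randomisation?** Medicine use is recorded (3.3.3), but no action is attached. The QTc limit (3.3.4) and the treating physician's discretion (section 6) act on the trial drug, not on the patient's own tablets. Patients discharged during the 15 days continue the trial drug at home with a diary.

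**3. Dose ceiling.** Inputs: own dose up to 400 mg a day (section 2.1); trial dose 200 mg × 2 = 400 mg a day for 15 days (3.3.4).

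- Daily: 400 + 400 = 800 mg, against 400 mg planned.
- Over 15 days: 15 × 800 = 12,000 mg (12 g), against 15 × 400 = 6,000 mg (6 g).

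This is a ceiling. It applies to a user at the top of the range who is allocated to active drug and continues own supply throughout. The documents give no own dose for chloroquine, so no such sum is possible for it.

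**4. The plan's sample size.** Inputs from section 3.3.6: difference 1.5 days, SD 4 days, two-sided 5%, power 80%, t-test. The standardised difference is 1.5/4 = 0.375. The t-test needs 112.6 per arm, so 113 per arm and 226 in total, as the plan states. With 113 per arm the power is 80.14%. (The normal approximation gives 112 per arm, and 80.5% power at 113.) These figures are for a single-look test.

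**5. Effect on power.** Let *f* be the share of users in both arms. The documents give no value, so 0.1% to 2% is an assumption. As a worst case, suppose users show no treatment contrast at all. The mean difference becomes 1.5 × (1 − *f*), with SD 4 and 113 per arm unchanged.

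| *f* (assumed) | Users among 226 (226 × *f*) | Difference, days | Power |
|---|---|---|---|
| 0 | 0 | 1.5000 | 80.14% |
| 0.1% | 0.2 | 1.4985 | 80.06% |
| 0.5% | 1.1 | 1.4925 | 79.75% |
| 1% | 2.3 | 1.4850 | 79.35% |
| 2% | 4.5 | 1.4700 | 78.54% |

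The largest loss is 80.14 − 78.54 = 1.6 percentage points.

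**The case against.** The strongest reply accepts the omission and disputes its weight.

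- **Safeguards.** A physician takes all medical decisions (3.3.3), the interaction text is introduced as a non-exhaustive list, and the physician may withdraw a patient (section 13). Stopping the trial drug also ends the double dosing. This makes an overlooked overlap less likely, and once a stop rule is triggered the duplication does end. But these steps are discretionary or act only after exposure, and none prevents randomisation. After such a stop, own supply may still continue, which matters for the contrast.
- **QT risk.** Section 6 gives QT prolongation an unknown frequency for both drugs, and ties it to particular risk factors for hydroxychloroquine. In a long-term user the screening ECG would normally be recorded with own drug on board. That lowers the risk, but it does not test the added trial dose before it starts.
- **The 800 mg figure.** It needs several unlikely things at once. That is right, and it should be read only as a ceiling. The protocol says its hydroxychloroquine dosing follows the product summary. The summaries are not part of the two documents, so what they say on duplication cannot be judged here.
- **Validity.** Users would be few, and total loss of contrast is too harsh an assumption, since the arms still differ on azithromycin. Both points stand. The power figures are therefore a lower bound for the shares assumed, and the validity argument is minor.
- **Chloroquine.** The protocol documents long-term use for hydroxychloroquine only. That stands too. Naming chloroquine in the criterion is a precaution at no extra cost.

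**Conclusion.** The gap is real: no written rule keeps a current hydroxychloroquine or chloroquine user out of the trial, or makes such a patient stop own supply. Confidence in that reading is high, because it rests on the text of the criteria.

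The practical size is small. The number of users is unknown and probably low, and the 0.1–2% range is an assumption without a source in the documents. Within it the effect on power is negligible, and the sample size of 226 needs no change. What remains is an avoidable risk to individual patients, with a dose of up to twice the planned one as the extreme, and a control arm that may include someone on active drug. This is worth considering as a cheap improvement. It does not threaten the trial's conclusions.

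**What to change.** Add current treatment with hydroxychloroquine or chloroquine to the exclusion criteria in Protocol section 3.3, and add a matching field to the REDCap eligibility form in section 3.3.2. A pause rule like the one for azithromycin would also prevent double dosing, but a paused control patient would then go 15 days on placebo without long-term treatment. Exclusion avoids that.

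For patients already enrolled, count users per arm from the medicine list collected under section 3.3.3 and report the number.

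Cost: one eligibility line, one REDCap field and one count per arm. The downside is that a few hydroxychloroquine or chloroquine users can no longer be recruited.

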## Proactive Prophylaxis With Azithromycin and Chloroquine in Hospitalised Patients With COVID-19 (ProPAC-COVID)

- Neurogenic hearing loss
- Psoriasis
- Retinopathy
- Maculopathy
- Visual field changes
- Breastfeeding
- Severe liver diseases other than amoebiasis (spontaneous INR > 1.5)
- Severe gastrointestinal, neurological and hematological disorders (investigator-assessed)
- eGFR <45 ml/min/1.73 m^2
- Clinically significant cardiac conduction disorders/arrhythmias or prolonged QTc interval (QTc (f) of > 480/470 ms).
- Myasthenia gravis
- Treatment with digoxin\*
- Glucose-6-phosphate dehydrogenase deficiency
- Porphyria
- Hypoglycaemia (Blood glucose at any time since hospitalization of <3.0 mmol/L)
- Severe mental illness which significantly impedes cooperation
- Severe linguistic problems that significantly hinder cooperation
- Treatment with ergot alkaloids

\*The patient must not be treated with digoxin for the duration of the intervention. For atrial fibrillation/flutter, select according to the Cardiovascular National Treatment Guide (NBV): Calcium antagonist, Beta blocker, direct current (DC) conversion or amiodarone. In case of urgent need for digoxin treatment (contraindication for the aforementioned equal alternatives), the test drug should be paused, and ECG should be recorded daily.

### Drug Interactions

Interactions should be taken into account if the patient is taking other medications. For azithromycin, this includes antacids, ergotamine derivatives, colchicine and cyclosporine. For hydroxychloroquine, these include antidiabetic agents, tricyclic antidepressants, antipsychotics, halofantrine, cyclosporine, mefloquine, antiepileptic drugs, praziquantel and agalsidase.

